3.4. The Immunogenicity Analysis Set

The anti-drug antibody (ADA) analysis set will consist of all subjects who received any study drug and who had at least 1 non-missing ADA result after the first dose of the study drug. Subjects will be analyzed according to the treatment actually received.

The neutralizing antibody (NAb) analysis set (NAS) includes all subjects who received any study drug and who tested negative at all ADA sampling times or tested positive with at least 1 nonmissing result in the NAb assay after the first dose of the study drug. Subjects who are ADAnegative are set to negative in the NAb analysis set. Subjects will be analyzed according to the treatment actually received.

3.5. Subgroups

Subgroups are defined by key baseline factors recorded on the eCRF (unless otherwise specified) and listed as follows.

Subgroups to be considered for both efficacy and safety analyses:

- Age group (years; 18 to <50; ≥ 50)
- Sex (Male, Female)
- Ethnicity: Hispanic or Latino (Yes, No)

• Race (White, Other)

Subgroups to be considered for efficacy analysis only:

- Serum specific birch pollen IgE level at screening(<17.5 kUa/L; ≥17.5 kUa/L)
- Serum specific oak pollen IgE level at screening (<0.7 kUa/L; ≥0.7 kUa/L) (North America)
- History of asthma (Yes, No)
- Region (North America (NA), Europe (EU))
- Baseline sensitization status based on sIgE or SPT (only sensitized to birch and birch related allergens, sensitized to birch, birch related allergens and any of other allergens)

Note: birch and birch related allergens are listed as below based on sIgE and SPT:

	Birch	Birch-related
SPT	Birch	Alder
	Birch Silver	Alder Grey
sIgE	rBet v1	Hazelnut
	rBet v2	Hornbeam

4. ANALYSIS VARIABLES

4.1. Demographic and Baseline Characteristics

The following demographic and baseline characteristics variables will be summarized:

- Demographic variables:
 - Age at screening as a continuous variable
 - Age group (years; 18 to $<50, \ge 50$)
 - Sex (Male, Female)
 - Race (White, Black or African American, Asian, American indian or Alaska native, Native Hawaiian or other pacific islander)
 - Ethnicity (Hispanic/Latino: Yes or No)
 - Baseline Weight (kg)
 - Baseline Height (cm)
 - Region (NA, EU)
- Baseline characteristics:
 - Standard regional skin prick test (SPT) for birch (mm)
 - Serum birch pollen sIgE at screening
 - Serum oak pollen sIgE at screening (North America)
 - Serum Bet v1 sIgE at screening
 - Baseline FEV1
 - Baseline sensitization status based on sIgE or SPT (e.g. sensitization to birch and birch related allergens only, sensitization to birch, birch related allergens and any of other allergens)

4.2. Medical History

Medical history will be coded using Medical Dictionary for Regulatory Activities (MedDRA[®]).

4.3. **Pre-treatment / Concomitant Medication and Procedures**

Medications/Procedures will be recorded from the day of informed consent until the end-of-study (EOS) visit. Medications will be coded using WHO Drug Dictionary (WHODD). Subjects will be counted once in each medication class linked to the medication.

Pre-treatment medications/procedures: medications taken or procedures performed prior to administration of the study drug.

Concomitant medications/procedures (CMs/CPs): medications taken or procedures performed following the dose of study drug through the EOS visit.

CONFIDENTIAL

Page 29 of 35

4.4. Prohibited or Rescue Medication/Procedure

4.4.1. **Prohibited Medications**

Preceding screening

Use of the below concomitant medications is prohibited within the following time period preceding the screening and randomization visits:

- Topical or systemic first generation H1 antihistamines (eg, diphenhydramine and chlorpheniramine) (3 days)
- Second generation and long-acting H1 antihistamines (eg, cetirizine) (5 days)
- Cromoglycates (14 days)
- Leukotriene modifiers (30 days)
- Intranasal corticosteroids (14 days)
- Systemic steroid treatment (30 days)
- Topical steroids, with the exception of hydrocortisone ($\leq 1\%$) (48 hours)
- Anticholinergics (eg, Ipratropium [Atrovent 40 µg]) (12 hours)
- Intramuscular corticosteroids (3 months prior to screening and during the study)
- Systemic or topical calcineurin inhibitors (14 days prior to screening and during the study)
- Topical or oral decongestants (72 hours)
- Tricyclic antidepressants/typical antipsychotics (14 days)
- Birch-specific allergen immunotherapy (5 years)
- Immune-directed biologic therapies that would interfere with Type 2 allergic disease or suppress the immune system (6 months)
- Long-acting anti-muscarinic agents (7 days)
- Ultra-long-acting β -agonists (eg, indacaterol, vilanterol, olodaterol) (14 days)
- Methylxanthines (eg, oral theophylline) (24 hours)

Preceding the end of study visit

Use of the below medications is prohibited within the following time period preceding the end of study visit.

- Desloratadine (5 days)
- Olopatadine (5 days)
- Topical steroids, with the exception of hydrocortisone ($\leq 1\%$) (48 hours)

Any time throughout the study

- Anticholinergics
- Leukotriene modifiers
- Cromoglycates
- Topical or oral decongestants
- Systemic steroid treatment
- Tricyclic antidepressants/typical antipsychotics
- Any allergen immunotherapy
- Immune-directed biologics therapies that would interfere with Type 2 allergic disease or suppress the immune system
- Methylxanthines (eg, oral theophylline)
- Anti-allergic medications (antihistamines, anti-allergic eye drops, anti-allergic nasal sprays) outside of study-related anti-allergic medications as they will be supplied as part of the study

Blinded adjudication of prohibited medications will be implemented before the database lock by the study medical director, considering the type of medication, indication, timing, frequency and the potential impact of the use of the prohibited medication. The adjudication procedure will be documented.

4.4.2. **Rescue medication**

Subjects will be provided with the following medications to treat allergic symptoms during the study:

- Desloratadine 5 mg (second generation antihistamine)
- Olopatadine 1 mg/mL (antihistamine eye drop)
- Mometasone furoate 50 ug/dose (intranasal steroid)

From the time of study drug dosing throughout the birch pollen season, subjects will be asked to record their daily medication use using an e-diary, including information regarding which medications was used and the amount of the pre-specified medications that was used. Utilization of rescue medications should be initiated when subjects reach a symptoms threshold of approximately TSS \geq 4/18. Subjects will be provided with training to understand the severity of symptoms associated with a TSS \geq 4/18.

Subjects should be instructed not to utilize rescue medications in the anticipation of the birch pollen season. Subjects should also be instructed not to utilize antihistamines (ie, desloratadine or olopatadine) for 5 days before the end of study visit.

4.5. Efficacy Variable

4.5.1. Primary Efficacy Variable

The primary efficacy endpoint in the study is the daily CSMS, averaged over the duration of the birch pollen season, in subjects who receive a single dose of REGN5713-5714-5715 versus placebo. Details of duration of birch pollen season are described in section 4.10.

Total Nasal Symptom Score (TNSS)

The TNSS ranges from 0 to 12 and is based on assessment of 4 nasal symptoms graded on a Likert scale ranging from 0 (none) to 3 (severe) for congestion, nasal itching, and rhinorrhea, and for sneezing. The TNSS will be recorded daily using an e-diary.

The average TNSS will be calculated using all observed daily scores during birch pollen season.

Total Ocular Symptom Score (TOSS)

The TOSS ranges from 0 to 6 and is based on 2 symptoms: itching/redness/gritty feeling and tearing/watering. Each of the 2 symptoms is graded 0 (absent), 1 (mild), 2 (moderate), or 3 (severe). The TOSS will be recorded daily using an e-diary.

If a patient has at least 1 TOSS during the birch pollen season, average TOSS will be calculated using all observed daily scores during birch pollen season.

If a patient has no TOSS during the birch pollen season, the mean of average TOSS during birch pollen season in the treatment group that the patient is randomized to will be used for the missing.

Total Symptom Score (TSS)

The daily TSS is calculated by adding the TNSS and TOSS together, for a combined TSS of 0 to 18 if both of them are not missing.

The average TSS will be calculated by adding average TNSS and average TOSS during birch pollen season. Imputed TOSS will be used if all TOSS data were missing (described above).

Daily Medication Score (DMS)

Subjects will be asked to record their daily rescue medication use using an e-diary, including which medications and the amount of these pre-specified medications. This information will be used to calculate the DMS as follows: desloratadine 5 mg 6 points/dose; maximum daily score 6 points, olopatadine 1 mg/mL each drop 1.5 points/drop; maximum daily score 6 points, mometasone furoate 50 ug/dose 2.0 points/spray; maximum daily score 8 points). The maximum DMS score is 20.

The average DMS will be calculated using the same method as described for TOSS.

Combined Symptom and Medication Score (CSMS)

The daily CSMS is calculated by adding the DMS and TSS together, with scores ranging between 0 and 38 if both of them are not missing.

The average CSMS will be calculated by adding average TNSS, average TOSS and average DMS during birch pollen season. Imputed TOSS and/or DMS will be used if missing is occurred.

CONFIDENTIAL

Page 29 of 35

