2.3. Sample Size and Power Considerations

This study is powered to detect differences between REGN5713-5714-5715 and placebo on the primary endpoint of the average CSMS during birch pollen season. A sample size of 120 subjects per arm gives 90% power to detect a mean difference in average CSMS of 1.9 (30% reduction from placebo) in REGN5713-5714-5715 (mean CSMS = 4.4) and placebo (mean CSMS = 6.3),

assuming a common standard deviation in CSMS of 4.5 with a two-sample t-test at 2-sided significance level of 0.05. Assuming 20% drop out rate during the birch pollen season, the target is to randomize 150 subjects per arm.

Estimates of mean and variability of the CSMS are based on pooled estimates across several field studies for grass sublingual immunotherapy, and a 30% treatment effect relative to placebo is in line with what was observed in the phase 1b POC study for REGN5713-5714-5715.

This planned sample size (150 subjects per arm) also gives 93% power to detect a mean difference in TNSS of 0.6 (26% reduction from placebo) in REGN5713-5714-5715 (mean TNSS=1.7) and placebo (mean TNSS=2.3), assuming a common standard deviation in TNSS of 1.5 at 2-sided alpha of 0.05 using a two-sample t-test. The assumptions of TNSS endpoint are based on effects observed in the GT-08 trial of timothy grass sublingual tablet (Dahl, 2006). With the same mean for placebo and common standard deviation from GT-08 but a 30% reduction from placebo for REGN5713-5714-5715 as observed in the phase 1b POC study, the study will have a greater power.

The sample size and power calculations were performed using nQuery Advisor 7.0

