3.1. The Full Analysis Set (FAS)

The full analysis set (FAS) includes all randomized subjects who had at least 1 e-diary entry with symptoms or medication score recorded during the birch pollen season; it is based on the treatment allocated (as randomized). Since the TNSS, TOSS and DMS will be completed sequentially, all randomized subjects with at lease 1 TNSS e-diary entry will be included in FAS. Efficacy endpoints will be analyzed using the FAS.

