5.6.2. Analysis of Secondary Efficacy Variables

Secondary efficacy variables will be analyzed using linear mixed-effect model in the same fashion as the primary analysis for primary endpoint, average CSMS during birch pollen season. Subjects with at least 1 day of post-baseline diary record will be included in the analysis, and only days with observed data (including any available data of daily entries prior to subject discontinuation) will be included in the calculation of average score. Data after rescue will be utilized and data after relevant prohibited medications will be set to missing according to Table 2.

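### Filling a wholly missing season of TOSS or DMS with the subject's own-arm mean, analysed as observed, understates the standard error and conflicts with SAP 5.6.2 and the protocol

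*SAP*

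**What the plan says.** SAP 4.5.1 averages whatever TOSS days a subject has. If there are none in the season, the subject is assigned "the mean of average TOSS during birch pollen season in the treatment group that the patient is randomized to". For medication use, "The average DMS will be calculated using the same method as described for TOSS". A filled TOSS is carried into average TSS, and for CSMS "Imputed TOSS and/or DMS will be used if missing is occurred". Table 1 in SAP 5.6 repeats the rule for the primary estimand.

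The rule can be reached because one TNSS entry is enough for the FAS. SAP 3.1 gives the reason: "Since the TNSS, TOSS and DMS will be completed sequentially". A subject can therefore have TNSS but no TOSS or DMS.

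SAP 5.6.1 puts one average per subject into a linear mixed model and reports LS-means, a confidence interval and a p-value. It describes no multiple imputation or variance adjustment. Table 1 and 5.6.1 use the same device for the entire average CSMS when prohibited medication leaves a subject with no usable data.

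Other sections differ:
- SAP 5.6.2, on the secondary averages: "only days with observed data (including any available data of daily entries prior to subject discontinuation) will be included".
- SAP 6.3 refers to 4.5.1 and 4.5.2 for missing-data rules for both primary and secondary variables. Only 4.5.1 contains any.
- Protocol 11.4.3.1 says the primary endpoint needs no imputation. SAP 1.2.3, which lists departures from the protocol, mentions only the removal of the per-protocol set.
- SAP 5.6.1 describes a CSMS sensitivity analysis, but the table in SAP 10.1.1 shows none for CSMS.

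**The concern.** A value set to its own arm's mean adds no information about that component. It adds one to the sample size and nothing to the spread, so the reported standard error is too small whenever the rule is used. The rule also assumes that a subject who never reported the component had exactly the average outcome of the assigned arm, and so the full arm effect.

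CSMS, TSS, TOSS and DMS are steps 1, 3, 6 and 7 of the hierarchy in SAP 5.6.3, which claims overall control at 0.05. Separately, two programmers following different sections could produce different TSS, TOSS and DMS results from the same data.

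**Working it through.** **Plan's own figure.** SAP 2.3: "A sample size of 120 subjects per arm gives 90% power to detect a mean difference in average CSMS of 1.9", "assuming a common standard deviation in CSMS of 4.5 with a two-sample t-test at 2-sided significance level of 0.05". The standard error is 4.5 × √(2/120) = 0.581, and 1.9/0.581 = 3.27. Power is Φ(3.27 − 1.96) = 0.905, or 0.903 by the noncentral t. Dropout: 120/0.8 = 150. The minimum significant difference is 1.144, against the protocol's 1.14. The stated design reproduces.

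**Inputs not in the documents.** The share m of subjects with a component wholly missing, and the SDs of TOSS and DMS, are not given. The ranges below are assumptions. Missing subjects are taken as a random subset of their arm.

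**TOSS or DMS as the endpoint.** With n per arm and a share m set to the arm mean, the reported variance of the mean is about (1−m)σ²/n. The true variance is σ²/[(1−m)n]. So reported SE / true SE = 1−m, and the actual two-sided error is 2 × [1 − Φ(1.96 × ratio)]. At m = 5%: 2 × [1 − Φ(1.862)] = 0.063.

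**CSMS = A (observed) + B (filled).** With variances VA and VB and covariance C:

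ratio² = [VA + (1−m)VB + 2(1−m)C] / [VA + VB/(1−m) + 2C]

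Example: B is half the variance, C = 0, m = 5%. The numerator is 0.5 + 0.475 = 0.975, the denominator is 0.5 + 0.5/0.95 = 1.026, the ratio is 0.975 and the error is 0.056. The CSMS column takes B as 5 to 50% of VA + VB and a correlation of 0 to 0.6.

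| m | SE ratio, TOSS or DMS | Error, TOSS or DMS | Error, CSMS |
|---|---|---|---|
| 1% | 0.99 | 0.052 | 0.050–0.051 |
| 2% | 0.98 | 0.055 | 0.050–0.052 |
| 5% | 0.95 | 0.063 | 0.051–0.056 |
| 10% | 0.90 | 0.078 | 0.051–0.063 |

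If TOSS and DMS are missing together, B is their sum and could exceed half the variance. For non-negative correlation the TOSS or DMS column is then the ceiling for CSMS.

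**Simulation check.** Two-sample t-test, 150 per arm, 20,000 null runs, with 3, 8 or 15 subjects per arm filled (2, 5 and 10%, rounded to whole subjects). Rejection for the filled component was 0.056, 0.063–0.066 and 0.078. For CSMS, with B at 15% or 50% of the variance and correlation 0.3, it was 0.051–0.053, 0.052–0.056 and 0.056–0.063. Leaving the affected subjects out gave 0.048–0.051 for m from 2 to 20%.

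**Point estimate.** With a true difference of 1.9 (10,000 runs), the mean estimate was −1.898 imputed, −1.897 to −1.898 with full data and −1.898 to −1.899 complete-case. At m = 5%, power was 0.954 imputed and 0.943 complete-case.

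**If missingness is not random.** Suppose missing active-arm subjects truly resembled placebo on the component. The own-arm mean then overstates the effect by m times the component effect. If the component carried half of 1.9, that is 0.02 × 0.95 = 0.019 at m = 2%.

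**The case against.** The trigger is narrow. A single TOSS entry in the season switches the rule off, so a filled subject must have completed TNSS at least once and never the next item. Nothing in the documents suggests that 5 or 10% would do so. This stands: the small shares are the more plausible ones, although that is an inference.

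The larger error rates belong to TOSS and DMS, the last two steps of the hierarchy, and arise only if 4.5.1 overrides 5.6.2. This also stands. One could reconcile the two by reading 5.6.2 as a rule about days and 4.5.1 as a rule for subjects with no days, but the SAP does not say so. For TSS, 4.5.1 explicitly uses the filled TOSS.

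The CSMS sensitivity analysis in SAP 5.6.1 avoids the arm mean. It scores missing TOSS or DMS as 0 on days with TNSS and leaves out subjects without data. It is a partial safeguard: it also changes the handling of prohibited-medication days, so it does not isolate this rule, and it does not cover TSS, TOSS or DMS.

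A reader might infer that the rule enlarges the treatment difference, or that using the assigned arm is itself the error. Neither follows. Each arm's component mean stays at its observed value, and a sound multiple imputation would also condition on treatment. The defect is that the uncertainty of the filled value is ignored. Nor does the subject contribute nothing: the observed TNSS remains in CSMS and TSS.

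**Conclusion.** The rule is wrong as written and should be changed, but the likely harm to the primary result is small. Under random missingness the estimate is unaffected and the reported precision is too high. With 2% or fewer filled, the CSMS error is about 0.050 to 0.052 under the variance shares assumed, with a ceiling of 0.055. For TOSS and DMS it is 0.052 to 0.055 at 1 to 2%, and 0.063 to 0.078 at 5 to 10%, if 4.5.1 governs.

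These figures rest on an assumed m and on an unadjusted comparison. With strata and pollen region in the model they are approximate. The documents do not support a claim that the primary p-value is materially invalid.

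The whole-CSMS version of the device is stronger per subject, because the 1−m ratio then applies directly to the primary endpoint. The conflicts between sections need resolving whatever m turns out to be.

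**What to change.** - Delete the own-arm-mean rule from SAP 4.5.1 and Table 1.
- For TOSS and DMS as endpoints, analyse subjects with observed data, as 5.6.2 says, and state this as an exception to the FAS.
- For TSS and CSMS, multiply impute the missing component from the subject's own TNSS, the stratification factors, pollen region and treatment, and combine by Rubin's rules. This keeps the observed TNSS.
- Replace the whole-CSMS own-arm-mean imputation in Table 1 and 5.6.1 with a method that also carries imputation uncertainty.
- Report the number of subjects imputed, by arm and component.
- Reconcile protocol 11.4.3.1 with SAP 1.2.3, 4.5.1, 5.6.2, 6.3 and 10.1.1. Record the departure from the protocol and list the CSMS sensitivity analysis in the appendix table.

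The cost is SAP wording, modest programming and slightly wider intervals. For scale, leaving affected subjects out of CSMS at 5% missing gave simulated power of 0.943 with 150 per arm, against about 0.95 with nothing missing.

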1.2.4. Revision History for SAP Amendments

The purpose of this amendment is to update the intercurrent events strategy for use of prohibited medications per FDA's suggestion. A composite strategy will be applied only for the use of

systemic steroids and Type 2 biologics. For the other prohibited medications, a treatment policy will be applied.

Section	Description of Additions/Updates	
Section 5.6 Table 1	• Update the intercurrent events strategy for use of relevant prohibited medications	
Section 5.6.1 Table 2	• Update the list of relavant prohibited medications that will affect efficacy	

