4.5.2. Secondary Efficacy Variables

The secondary efficacy endpoints are:

- TSS, TNSS, and TOSS, averaged over the duration of the birch pollen season, in subjects who receive a single dose of REGN5713-5714-5715 versus placebo
- DMS, averaged over the duration of the birch pollen season, in subjects who receive a single dose of REGN5713-5714-5715 versus placebo
- Change and percent change from baseline to the end of study in birch SPT mean wheal diameter in subjects who receive a single dose of REGN5713-5714-5715 versus placebo
- The number of "well days" in each of the treatment groups, where the "well days" are defined as days when rescue medication is not utilized and the TSS is $\leq 2/18$

Birch Allergen and Standard Regional Skin Prick Tests

An SPT with birch allergen extract and a regional SPT (such as with dust mites, grasses, ragweed, other trees, including other birch homologous trees [such as alder and oak], mold, cat, and dog) will be performed to assess sensitization status. Skin prick test data may be used to determine the relationship between birch and regional allergen sensitization at baseline and pharmacodynamic effects of REGN5713-5714-5715 to reduce allergic symptoms upon birch pollen allergen challenges. Mean wheal diameter is measured approximately 15 minutes after placement. Aside from the birch skin test requirement for enrollment (which is >=5mm compared to the negative control), a positive response is defined by a mean wheal diameter at least 3 mm greater than a negative control.

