5.6.1. Analysis of Primary Efficacy Variable

The primary analysis will focus on the comparison between the REGN5713-5714-5715 arm and placebo arm. The average CSMS during birch pollen season will be compared in subjects receiving REGN5713-5714-5715 and subjects receiving placebo using a linear mixed-effect model, with the treatment group and randomization stratification factors (serum specific birch pollen IgE levels at screening (<17.5 kUa/L, \geq 17.5 kUa/L), serum specific oak pollen IgE levels at screening (<0.7 kUa/L, \geq 0.7 kUa/L for NA) and geographical region (NA, EU)) as fixed effects and pollen region as a random effect, to account for potential differences in birch pollen seasons based on the geographical location of each pollen region. Subjects with at least 1 day of post-baseline diary record with CSMS during the birch pollen season. The least squares means (LS-means) estimate for each treatment, and LS-means for between-treatment difference with its 95% confidence interval and p-value will be provided.

The average CSMS will be calculated based on total symptom score (TNSS and TOSS, max of 18/day) and daily medication score (max of 20/day) recorded over the duration of the birch pollen season. The start and end of the birch pollen season is defined in section 4.10 for each site based on the local pollen counts.

Data after any rescue medication use will be used for the calculation of the average CSMS, but relevant prohibited medications that may have an impact on symptom measurements will result in subsequent symptoms and medication scores not be utilized in the CSMS for that subject for a specified period of time (determined by medication type). The prohibited medications will be adjudicated by study medical monitor before the database lock. A list of those relevant prohibited medication and the rules of data utilization are detailed in Table 2.

Table 2: Data Utilization for Relevant Prohibited Medications

Name of Medication	Rule of Data Utilization
Systemic steroids (oral/ IV/ IM/ intra-articular/ other)	Data will not be used after the
Type 2 Biologics	medication usage.

In additional, if a patient has major change in birch pollen exposure (e.g. travel out of country), the data will be set to missing during this major change and no imputation will be applied.

For patients with data not utilized due to prohibited medication, the following data imputation rule will be apply:

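### The medication score and the well-day rule count only the three supplied rescue products, so a day controlled by a subject's own antihistamine can score no medication points and count as a well day

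*SAP*

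**What the plan says.** SAP 4.5.1 has subjects enter their daily rescue use in the e-diary, "including which medications and the amount of these pre-specified medications". Points go to three products, the first being "desloratadine 5 mg 6 points/dose; maximum daily score 6 points". Olopatadine drops are capped at 6 points and mometasone sprays at 8, so the DMS maximum is 20. SAP 4.4.2 lists these same three products, supplied by the study, as the rescue medication.

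SAP 4.4.1 prohibits throughout the study "Anti-allergic medications (antihistamines, anti-allergic eye drops, anti-allergic nasal sprays) outside of study-related anti-allergic medications". It adds a blinded adjudication of prohibited medication before database lock.

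SAP 1.2.4 records that the amendment keeps a composite strategy for systemic steroids and Type 2 biologics only, and continues: "For the other prohibited medications, a treatment policy will be applied". Table 2 in SAP 5.6.1 lists just those two classes. SAP 5.6.2 carries the table over to the secondary endpoints: "data after relevant prohibited medications will be set to missing according to Table 2".

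SAP 4.5.2 has well days "defined as days when rescue medication is not utilized and the TSS is" at most 2 out of 18. SAP 5.3 summarises prohibited medication for the study total, not by arm.

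**The concern.** A combined symptom and medication score adds medication to symptoms so that relief bought with a drug is not read as absence of disease. Here the medication part depends on where the drug came from. An antihistamine from the study supply costs 6 points. One from the subject's own cupboard costs nothing if no supplied product is used that day, although it may lower the symptom score just as much.

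The well-day rule has the same gap, because its only medication test is for rescue medication, and the only list of that is the three supplied products.

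Adjudication does not close the gap. It can identify off-supply use, but no scoring or data rule then applies to these classes. The primary endpoint (CSMS), the DMS (seventh in the testing order of SAP 5.6.3) and well days could each depend partly on off-supply use. Because prohibited medication is tabulated for the study total, an imbalance between arms would not show in the planned summary.

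**Working it through.** **1. The plan's own figures.** Inputs from SAP 2.3: means 4.4 and 6.3, difference 1.9, SD 4.5, 120 evaluable per arm, two-sided 0.05, 20% dropout. Standard error = 4.5 × √(2/120) = 0.581. Power is 90.5% by the normal approximation and 90.3% by the noncentral t, against the stated 90%. The required size is 118 per arm, against 120 stated. Randomised: 120 / 0.80 = 150 per arm. Score ranges: DMS 6 + 6 + 8 = 20 and CSMS 18 + 20 = 38. All agree with the SAP.

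**2. One day under the written rules.** Take a day with TSS 2.

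| Antihistamine taken | DMS | CSMS | Well day? |
|---|---|---|---|
| One supplied desloratadine dose | 6 | 2 + 6 = 8 | No |
| Own antihistamine, no supplied product | 0 | 2 + 0 = 2 | Yes |

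The gap on that day is 6 points, or 6 / 1.9 = 3.2 times the planned mean difference. If supplied desloratadine is also taken that day, the class cap of 6 is already reached and nothing is lost.

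**3. Effect on the season average.** The documents give no rate of off-supply use, so the rates below are assumptions. Let f be the net excess, in one arm, of season-days on an own antihistamine that each lose the full 6 points. Symptom scores, SD 4.5 and 120 per arm are held fixed.

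Excess in placebo: difference = 1.9 − 6f.

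| f | Difference | Power (noncentral t) |
|---|---|---|
| 0 | 1.90 | 90% |
| 2% | 1.78 | 86% |
| 5% | 1.60 | 78% |
| 10% | 1.30 | 61% |
| 20% | 0.70 | 22% |

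Excess in active with no true effect: spurious benefit = 6f.

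| f | Spurious benefit | Chance of a significant result favouring active (nominal 2.5%) |
|---|---|---|
| 5% | 0.3 | 7% |
| 10% | 0.6 | 18% |
| 20% | 1.2 | 54% |

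**4. What those rates mean in subjects.** An excess of 5% of subjects using an own antihistamine on 20% of days is f = 0.05 × 0.20 = 1%, which gives 6 × 0.01 = 0.06 points, or 0.06 / 1.9 = 3% of the planned difference. An excess of 10% of subjects on 50% of days is f = 5%, which gives 0.30 points, or 0.30 / 1.9 = 16%. The larger values of f need heavy and lopsided use.

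**The case against.** The case against acting has several parts.

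- **An existing analysis may already cover it.** The sensitivity analysis in SAP 5.6.1 sets CSMS to missing on days touched by prohibited medication, and its wording is not confined to Table 2. On a plain reading it removes these days. This stands in part: the SAP does not say which medications are meant, Appendix 10.1.1 shows no sensitivity method for the primary endpoint, and the analysis covers neither DMS nor well days.
- **The strategy was deliberate.** SAP 1.2.4 says treatment policy was adopted at the FDA's suggestion, and Protocol 9.2.4.4 takes the point scheme from a cited source. A reader might infer that the primary CSMS should be re-scored. The documents do not support that. Concomitant medication is collected at contacts around days 28, 57, 85 and 113, about four weeks apart. SAP 6.3 can impute a missing start day to the first of the month and a missing end day to the last, so a few tablets could earn points for a whole month. This objection stands and limits the fix to sensitivity analyses.
- **Use may be rare.** All three classes are supplied, outside products are barred, and exclusion criterion 22 removes subjects unwilling to follow the medication rules. This is fair, and the frequency is unknown.
- **Well days carry little weight.** They are outside the testing hierarchy, and the note in SAP 1.2.2 refers to anti-allergy rescue medication, which might be read more widely. But no wider list is defined, and the endpoint is still reported.
- **Other classes share the gap.** Leukotriene modifiers, decongestants and cromoglycates are also prohibited, unscored and under treatment policy. This is true. They have no matching supplied product whose points could be borrowed.

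**Conclusion.** The gap is real but narrow. Followed exactly, the SAP gives a day on a subject's own antihistamine, with no supplied product used, 6 points less than a day on one supplied desloratadine dose, and can call it a well day.

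A reader might infer that the trial is biased towards no difference because symptomatic placebo subjects would reach for their own tablets. The documents do not establish this. Excess use in placebo would shrink the effect and excess use in active would inflate it. Nothing in either document gives a rate or says which arm would use more.

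The figures from 0.06 to 0.30 points, and the power figures, are illustrations. They assume the stated rates, the loss of the full 6 points on every such day, and unchanged symptom scores and SD. They show that a small imbalance matters little and a large one would matter. They do not show that either will occur. Treatment policy for these medications is not itself an error. What is missing is a well-day rule that recognises such use, a sensitivity analysis with a clear scope, and a display by arm.

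**What to change.** Keep the primary CSMS and the treatment-policy strategy as written, and make three changes before database lock.

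1. **SAP 4.5.2.** Define a well day as TSS of 2 or less with no supplied rescue medication and no adjudicated off-supply anti-allergic medication recorded for that day.
2. **SAP 5.6.1.** State that the sensitivity analysis that sets prohibited-medication days to missing includes off-supply antihistamines, eye drops and nasal sprays, not only the Table 2 classes. Add a second sensitivity analysis that gives those days the points of the matching supplied class, within the caps of 6, 6 and 8. Enter both in Appendix 10.1.1, which now shows none.
3. **SAP 5.3.** Summarise prohibited anti-allergic use by treatment arm, not for the study total only.

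The cost is SAP text and a derivation from concomitant-medication records that are already collected and adjudicated blind. The downside is precision: dates and amounts in those records are less exact than the e-diary. Only adjudicated records with known dates should be used, without the imputed dates of SAP 6.3. A convention for the amount taken (one dose or the daily class cap) must be stated in advance.
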